2. INVESTIGATION PLAN

2.1. Study Design and Randomization

This is a phase 3, randomized, double-blind, parallel-group, multi-dose study in approximately 630 cat-allergic adult and adolescent patients (ages ≥ 12 to < 18 years), where permitted, with allergic rhinitis with or without conjunctivitis and with or without asthma.

- Screening period of up to 12 weeks: Cat allergic patients living with a cat who are significantly symptomatic while using standard of care anti-allergy medications will be enrolled in the study. The study includes a screening period of up to 12 weeks to ensure sensitization, symptom and medication use requirements are met during the baseline period.
- Randomization to 1 of 2 treatment arms (1:1)
 - REGN1908-1909 600 mg Q12W (300 mg per mAb)
 - Placebo that replaces REGN1908-1909
- Study drug period (60 weeks \pm 7 days): to administer patients with R1908-1909 or placebo dose regimen every 12 weeks (Q12W) for a total of 5 administrations
- Post treatment period (12 weeks \pm 7 days): to continue to collect safety data (PK, immunogenicity, etc.) after patients have completed the study drug treatment

Efficacy will be evaluated by assessing the reduction of allergic nasal and ocular symptoms and the reduction in the use of allergy rescue medications during the initial 12 weeks and the last 12 weeks. The primary efficacy endpoint will be assessed during the last 12 weeks of treatment (weeks 48-60).

The initial 12 weeks of the treatment period are defined as the date of Visit 3 through Visit 6.

The last 12 weeks of the treatment period are defined as the date of Visit 12 through Visit 14.

The incidence and severity of TEAEs, including hypersensitivity reactions and local injection site reactions, will also be assessed throughout the study. Total drug concentration in serum and immunogenicity of REGN1908, and REGN1909 will also be measured throughout the study.

There will be a non-binding futility interim analysis (IA) in the study planned to be performed when at least 40% of randomized patients have completed the week 12 visit or discontinued before week 12.

Randomization will be stratified by IVRS based on the following:

- Age (adolescents vs adults)
- Asthma status (yes vs no)
- House dust mite (HDM) sensitivity (< 0.7 kUa/L versus ≥ 0.7 kUa/L)

2.2. Statistical Hypothesis

For comparison of REGN1908-1909 to placebo, the following hypothesis of the primary endpoint (the average daily CSMS over the last 12 weeks of the treatment period [weeks 48 to 60]) will be tested:

- H_0 : There is no difference in CSMS, averaged over the last 12 weeks of the treatment period (weeks 48 to 60), in patients receiving REGN1908-1909 and placebo.
- H_1 : The CSMS, averaged over the last 12 weeks of the treatment period (weeks 48 to 60), is different in patients receiving REGN1908-1909 and placebo.

The statistical hypothesis specified above can be tested on the secondary endpoints of clinical interest. The study will be declared positive if the null hypothesis for the primary efficacy endpoint for REGN1908-1909 versus placebo is rejected.

2.3. Sample Size and Power Considerations

The sample size will be approximately 315 patients per arm, for a total of 630 patients in two treatment groups. This study is powered to detect the difference between REGN1908-1909 and placebo on the primary endpoint of daily CSMS averaged over the last 12 weeks of the treatment period (weeks 48 to 60) when considering a 20% dropout rate by week 60.

A sample size of 251 patients per arm gives 90% power to detect a mean difference in daily CSMS, averaged over weeks 48-60, of 1.8 (20% reduction from placebo) between REGN1908-1909 (mean CSMS=7.3) and placebo (mean CSMS=9.1), assuming a common standard deviation in CSMS of 6.2. Assuming a 20% dropout rate (~64 per arm), the sample size is 315 per arm. A 2-sample t-test with 2-sided alpha of 0.049 was assumed (an administrative penalty of 0.001 will be taken from the significance level used at final analysis due to a planned interim analysis; details are provided in Section 7). Calculations were performed using nQuery+nTerim 4.0.

The sample size of 315 patients per arm also gives the power of 91% and 96% to detect a 20% reduction from placebo in TSS (SD=3.0 and mean in placebo=4.2) and daily TNSS (SD=2.3 and mean in placebo=3.3) averaged over the last 12 weeks (weeks 48 to 60), respectively. Details are displayed in Table 1.

Table 1: Summary of Statistical Assumptions and Power for Select Secondary Endpoints

Daily Score, Averaged over last 12 weeks	Mean		Anti-Fel d 1 vs Placebo		Power with n=315/arm*	Power with n=251/arm*
	Placebo	Anti-Fel d 1	% Reduction from Placebo	Reduction from Placebo (SD)		
TNSS	3.3	2.6	-20%	-0.7 (2.3)	96%	92%
TSS	4.2	3.4	-20%	-0.8 (3.0)	91%	84%

*: Two-sided t-test with alpha = 0.049, assuming 20% reduction from PBO

The assumptions of mean in the placebo and common standard deviation for the above endpoints are based on the house dust mite (HDM) SLIT-tablet data for combined rhinoconjunctivitis score during 8-week assessment period. A treatment difference of 20% relative to placebo is based on a previous phase 1b study (R1908-1909-ALG-1325) of the same molecules and the treatment effect observed for reduction in symptoms after a nasal allergen challenge over a 12-week period.

The sample size may be re-estimated in a blinded fashion after greater than 50% of patients have baseline data available using observed values of CSMS to determine the baseline placebo mean (SD) and assuming the same 20% difference between REGN1908-1909 versus placebo. If the re-estimated number is higher than the current estimation of 315 per arm, then the sample size may be increased. Further details are provided in Section 5.12.

[figure not shown]

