5.12. Sample Size Adjustment

Once at least 50% of patients are enrolled, if the observed blinded standard deviation (SD) for CSMS during the initial 12 weeks is greater than a 5% increase over the assumed SD (6.2), sample size may be increased accordingly, see Appendix Section [10.6](#). If the SD is lower than the current assumption (6.2), then no adjustment will be made. Similar methods may be considered if the SD of TNSS is larger than a 5% increase over the assumed SD (2.3).

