10.6. Additional Details on Sample Size Adjustment

The table below provides power and sample size calculations based on various observed values of standard deviation of CSMS and TNSS. These calculations may be used as a guide if a sample size adjustment is deemed necessary.

Endpoint (mean in protocol)	Observed SD (% of the SD in protocol)	Effect size	Power with current planned sample size* [±]	Sample size [% increase from protocol] required for 90% power* [¥]
CSMS (9.1)	6.2 (as assumed in protocol)	0.293	90%	315 [as assumed in protocol]
	6.5 (4.8% increase)	0.280	87%	346 [10%]
	6.8 (10% increase)	0.267	83%	379 [20.3%]
	7.1 (15% increase)	0.256	80%	413 [31.1%]
	7.4 (20% increase)	0.246	77%	449 [42.5%]
TNSS (3.3)	2.3 (as assumed in protocol)	0.29	89%	323 [2.5%]
	2.4 (4.3% increase)	0.28	86%	346 [10%]
	2.5 (10% increase)	0.26	83%	382 [21.3%]
	2.65 (15% increase)	0.25	79%	428 [35.9%]
	2.8 (20% increase)	0.24	74%	478 [51.7%]

*: Two-sided t-test with alpha = 0.049, assuming 20% reduction from PBO (mean difference = 1.8 for CSMS and 0.66 for TNSS)

[figure not shown]
±: Power assuming sample size = 251/arm (assuming 315/arm are enrolled and a 20% dropout rate)

¥: Sample size is inflated to account for a 20% drop-out rate

Signature Page for VV-RIM-00201802 v2.0

Approval/eSignature		
---------------------	--	--

18-Aug-2022 21:50:37 GMT+0000

Approval/eSignature		
---------------------	--	--

19-Aug-2022 01:58:04 GMT+0000

Approval/eSignature		
---------------------	--	--

19-Aug-2022 12:17:52 GMT+0000

Approval/eSignature		
---------------------	---	--

19-Aug-2022 12:50:55 GMT+0000

Approval/eSignature		
---------------------	--	--

19-Aug-2022 13:18:33 GMT+0000

Approval/eSignature		
---------------------	--	--

19-Aug-2022 13:21:30 GMT+0000

Signature Page for VV-RIM-00201802 v2.0 Approved

Signature Page for VV-RIM-00201802 v2.0

Approval/eSignature		
---------------------	--	--

19-Aug-2022 13:26:20 GMT+0000

Signature Page for VV-RIM-00201802 v2.0 Approved

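### SAP Table 1 and SAP 10.6 give different TNSS power (92% and 89%) for the same stated inputs, because Table 1 uses rounded differences that are not 20%

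*SAP*

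**What the plan says.** SAP 2.3 Table 1 lists two secondary endpoints, each labelled as a 20% reduction from placebo:

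- TNSS: means 3.3 and 2.6, difference 0.7, SD 2.3. Power is 96% at 315 per arm and 92% in the column headed "Power with n=251/arm".
- TSS: means 4.2 and 3.4, difference 0.8, SD 3.0. Power is 91% at 315 per arm and 84% at 251 per arm.

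The table's footnote reads "Two-sided t-test with alpha = 0.049, assuming 20% reduction from PBO".

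SAP 10.6 tabulates power and required size for a range of SDs. Its footnote has the same alpha and the same 20% reduction, and adds "mean difference = 1.8 for CSMS and 0.66 for TNSS". The basis for its power column is "Power assuming sample size = 251/arm (assuming 315/arm are enrolled and a 20% dropout rate", and for its size column "Sample size is inflated to account for a 20% drop-out rate". Its TNSS row at SD 2.3 shows 89% power and 323 per arm for 90% power.

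Protocol Table 4 prints the same rounded means and differences as Table 1. Protocol 11.2 and the synopsis quote the resulting 96% and 91%, at 315 per arm only, and state alpha 0.05 for the sample-size calculation. Protocol 11.4.4 sets 0.049 for the final analysis.

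**The concern.** Two tables in one SAP, under the same stated assumptions, give different answers to one calculation. Daily TNSS over weeks 48 to 60 is the second of 13 tests in the SAP 5.6.3 hierarchy, and every later test depends on it. A reader asking whether the planned size gives this endpoint 90% power is told yes by Table 1 (92%) and no by 10.6 (89%, with 323 per arm needed).

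SAP 10.6 is also the reference for any blinded increase in size, and SAP 5.12 extends that possibility to TNSS: "Similar methods may be considered if the SD of TNSS is larger than a 5% increase over the assumed SD (2.3"). Its entries therefore need to be reliable.

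**Working it through.** **Method.** Two-sample t-test, two-sided, equal arms, as both tables state. With n per arm and difference d, the noncentrality is d / (SD × √(2/n)) on 2n − 2 degrees of freedom. Power is the noncentral-t probability beyond the two-sided critical value. At alpha 0.049 the critical value is 1.973 for n = 251 and 1.972 for n = 315.

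**What 20% is.** TNSS: 0.20 × 3.3 = 0.66, whereas 0.7/3.3 = 21.2%. TSS: 0.20 × 4.2 = 0.84, whereas 0.8/4.2 = 19.0%.

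**Reproducing the printed powers, then using a true 20%** (alpha 0.049):

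| Endpoint, difference | Noncentrality, n=251 | Power, n=251 | Power, n=315 | Printed |
|---|---|---|---|---|
| TNSS, 0.70 | 0.70/(2.3×√(2/251)) = 3.41 | 92.43% | 96.75% | Table 1: 92%, 96% |
| TNSS, 0.66 | 0.66/(2.3×√(2/251)) = 3.21 | 89.25% | 94.81% | 10.6: 89% (n=251) |
| TSS, 0.80 | 0.80/(3.0×√(2/251)) = 2.99 | 84.45% | 91.51% | Table 1: 84%, 91% |
| TSS, 0.84 | 0.84/(3.0×√(2/251)) = 3.14 | 87.74% | 93.82% | not given |

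Each table follows from its own difference. Alpha does not explain the gap: TNSS with 0.66 at alpha 0.05 and 251 per arm gives 89.41%.

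**Sizes in SAP 10.6, TNSS rows** (d = 0.66, 90% power, alpha 0.049, evaluable n divided by 0.8):

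| SD | Evaluable n | n/0.8 | Printed |
|---|---|---|---|
| 2.3 | 258 | 322.5 | 323 |
| 2.4 | 281 | 351.25 | 346 |
| 2.5 | 305 | 381.25 | 382 |
| 2.65 | 342 | 427.5 | 428 |
| 2.8 | 382 | 477.5 | 478 |

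Four rows reproduce when rounded up. The row "2.4 (4.3% increase") does not. By the same rounding it should be 352, and 352/315 is an 11.7% increase. Its printed entry of 346 with a 10% increase is identical to the CSMS row at SD 6.5.

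**CSMS effect sizes in SAP 10.6.** At SD 6.2, 1.82/6.2 = 0.2935 and 1.8/6.2 = 0.2903; the table prints 0.293. The whole printed column (0.293, 0.280, 0.267, 0.256, 0.246) follows from 1.82, which is exactly 20% of 9.1. From the footnoted 1.8 the values are 0.290, 0.277, 0.265, 0.254 and 0.243. The CSMS sizes do follow from 1.8: at SD 6.2, 252 evaluable gives 252/0.8 = 315, where 1.82 would give 247 and 309.

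**Primary endpoint.** CSMS 1.8, SD 6.2, 251 per arm: 89.93% at alpha 0.049 and 90.08% at 0.05.

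**The case against.** The strongest reply is that no decision changes. The study is powered on CSMS, and neither document sets a 90% target for TNSS. SAP 5.12 triggers on the observed SD, not on power, and treats TNSS only as something that may be considered. The TNSS trigger is 2.3 × 1.05 = 2.415, so the faulty SD 2.4 row lies just below it. The hierarchy depends on significance at analysis, which a planning table does not alter. All of this stands and is why the point is minor.

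It can also be said that Table 1 shows its rounded means and differences openly, and that 1.8 for the primary is itself 19.8%. But Table 1's footnote claims a 20% reduction, and the same claim in 10.6 gives a different power. A footnote explaining the rounding would reconcile the SAP, but it would leave power figures that do not answer the question stated.

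Two further criticisms are fair and refine the correction:

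- The tables mix conventions. Several powers are truncated (96.75% is printed as 96%), while 89.93% is printed as 90%. Unrounded power against unrounded power, the effect of the difference alone is 3.2 points for TNSS (92.43 − 89.25) and 3.3 for TSS (87.74 − 84.45) at 251 per arm.
- Two TNSS labels in 10.6 are loose. SD 2.5 is 8.7% above 2.3, not 10%, and SD 2.8 is 21.7% above, not 20%.

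**Conclusion.** The concern holds and is minor. Compared with the printed figures, a true 20% reduction changes Table 1 as follows:

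- TNSS: 89.2% rather than 92% at 251 per arm (2.8 points too high), and 94.8% rather than 96% at 315 (1.2 too high).
- TSS: 87.7% rather than 84% at 251 per arm (3.7 too low), and 93.8% rather than 91% at 315 (2.8 too low).

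The second test in the hierarchy therefore has just under 90% power at the planned evaluable size, as 10.6 says. The size in the TNSS SD 2.4 row is 6 per arm too low. Primary power, the planned 315 per arm and the SD triggers are unaffected.

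These results rest on the documents' own unadjusted t-test, SDs, placebo means and 20% dropout. They do not assess whether those assumptions are realistic.

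**What to change.** 1. In SAP 2.3 and Table 1, and in Protocol 11.2, Table 4 and the synopsis, use differences of 0.66 and 0.84 (active means 2.64 and 3.36). State power at 251 per arm as 89% for TNSS and 88% for TSS. Label any figures at 315 per arm (95% and 94%) as assuming no dropout.
2. In Protocol 11.2 and the synopsis, change the sample-size alpha to 0.049 to match Protocol 11.4.4. The rounded powers and 315 per arm do not change.
3. Keep 1.8 for the primary and describe it as about 20% (19.8%).
4. In SAP 10.6, keep 89% and 323 at TNSS SD 2.3 and change the SD 2.4 size to 352 (11.7%). Print the CSMS effect sizes as 0.290, 0.277, 0.265, 0.254 and 0.243. Relabel SD 2.5 and SD 2.8 as 8.7% and 21.7% increases.
5. Use one convention across the edited tables: powers to the nearest percent and enrolled sizes rounded up. In 10.6 this also changes:
   - CSMS power at SD 6.8 and 7.1 to 84% and 81% (83.92%, 80.68%);
   - TNSS power at SD 2.4, 2.5 and 2.8 to 87%, 84% and 75% (86.57%, 83.72%, 74.76%);
   - the CSMS SD 6.5 size from 346 to 347 (277/0.8 = 346.25; 10.2% above 315).

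The cost is text and table edits only, with no change to patients, analysis or planned size. The visible downside is that stated TNSS power drops below 90%; stated TSS power rises from 84% to 88%. The Protocol edits can wait for its next amendment if SAP 1.2.4 records the difference meanwhile.

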2.4. Study Plan

The total study duration is approximately 72 weeks excluding screening (Figure 1). Efficacy assessments will be done during the initial 12 weeks (weeks 0 to 12) after the first dose and during the last 12-week period (weeks 48 to 60) after last dose (dose 5) of REGN1908-1909 or placebo. For those individuals with seasonal allergies, efficacy assessments will be timed by the investigational site to ensure that the assessments are outside of any relevant pollen seasons. Approximately 630 cat-allergic subjects will be randomized 1:1 to REGN1908-1909 or placebo.

A non-binding futility interim analysis (IA) in the study is planned to be performed when at least 40% of randomized patients have completed the week 12 visit or discontinued before week 12. More details are specified in Section 7.

The Schedule of Events table is presented in Section 10.2.

Figure 1: Study Flow Diagram

3. ANALYSIS POPULATIONS

In accordance with guidance from the International Conference of Harmonization of Technical Requirements for Registration of Pharmaceuticals for Human Use (ICH) guideline ICH E9 Statistical Principles for Clinical Trials ([ICH, 1998](#)), the following population of analysis will be used for all statistical analysis:

3.1. The Full Analysis Set (FAS)

The full analysis set (FAS) includes all randomized patients; it is based on the treatment allocated (as randomized). Efficacy endpoints will be analyzed using the FAS.

3.2. The Safety Analysis Set (SAF)

The safety analysis set (SAF) includes all randomized patients who received any study drug; it is based on the treatment received (as treated). Treatment administration and all clinical safety variables will be analyzed using the SAF.

For patients randomized to either placebo or REGN1908-1909, a patient will be considered as treated with REGN1908-1909 if they received at least one dose of REGN1908-1909. If the patient receives no doses of REGN1908-1909 throughout the study, the patient will be considered as treated with placebo.

3.3. The Pharmacokinetic Analysis Set (PKAS)

The PK analysis set (PKAS) includes all patients who received any study drug and who had at least 1 non-missing concentration result following the first dose of study drug. The PK analysis set is based on the actual treatment received (as treated) rather than as randomized.

For patients randomized to either placebo or REGN1908-1909, a patient will be considered as treated with REGN1908-1909 if they received at least one dose of REGN1908-1909. If the patient receives no doses of REGN1908-1909 throughout the study, the patient will be considered as treated with placebo.

3.4. The Immunogenicity Analysis Set

The ADA analysis set (AAS) includes all treated patients who received any amount of study drug (active or placebo [safety analysis set]) and had at least one non-missing ADA result following the first dose of study drug or placebo. The ADA analysis set is based on the actual treatment received (as treated) rather than as randomized.

The NAb analysis set (NAbAS) includes all treated patients (active or placebo) that are included in the ADA analysis set and that tested negative at all ADA sampling times or tested positive at one or more post-dose ADA sampling times and had at least one non-missing post-dose NAb result (either imputed or analysis result). Samples that tested negative for ADA are not assayed in the NAb assay and the corresponding NAb results are imputed as negative and included as such in the NAb analysis set. Patients in the NAbAS with multiple post-dose ADA results which consist of both imputed NAb-negative result(s) for ADA negative samples and only missing NAb results for all ADA-positive result(s), are set to NAb negative. Patients in the NAbAS that have at least one

post-dose positive NAb analysis result are set to NAb positive even if other NAb results are missing.

3.5. Subgroups

Subgroups are defined by key baseline factors recorded on the eCRF (unless otherwise specified) and listed as follows. The analysis for the subgroups defined may not be performed if the number of patients within the subgroup is small, e.g., <10 patients per treatment arm.

Subgroups to be considered for both efficacy and selected safety endpoints:

- Age group (≥ 12 to < 18 years (Adolescents), ≥ 18 to < 65 years, ≥ 65 years)
- Sex (Male, Female)
- Ethnicity (Hispanic or Latino: Yes, No)
- Race (White, Black, Asian, Other)
- Baseline cat dander IgE level (< 17.5 kUa/L, ≥ 17.5 kUa/L)
- Asthma status (based on collected medical history: Yes, No)

Subgroups to be considered for primary and key secondary efficacy endpoints:

- House dust mite (HDM) sensitivity (Dermatophagooides farina (Df) and Dermatophagooides pteronyssinus (Dp) sIgE < 0.7 kUa/L, Either Df or Dp sIgE ≥ 0.7 kUa/L)
- Region (Canada, United States, Europe)
- Number of cats at baseline (1, 2, > 2)
- Patient Global Impression of Severity (PGIS) at baseline (no symptoms/mild, moderate, severe)
- Prior cat immunotherapy (Yes, No)
- Baseline sensitization status based on sIgE or SPT (only sensitized to cat allergens (mono-sensitized), and those sensitized to other allergens including seasonal and perennial allergens)

Note: Cat allergens and other allergens are listed as below for SPT and sIgE:

	Cat allergens	Other allergens
SPT	Cat Hair	Seasonal allergens: Tree (mix) Grass (mix) Ragweed Perennial allergens: House Dust Mite (mix) Mold (mix) Dog
sIgE	Cat Dander Fel d 1 Fel d 2 Fel d 4 Fel d 7	Seasonal allergens: Timothy Grass Perennial allergens: Dog Dander Mite Df Mite Dp Alternaria tenus Cladosporium herbarum Cockroach German

4. ANALYSIS VARIABLES

4.1. Demographic and Baseline Characteristics

The following demographic and baseline characteristics variables will be summarized descriptively:

- Demographic variables:
 - Age at screening as a continuous variable
 - Age group (Adolescents, Adults)
 - Sex (Male, Female)
 - Race (White, Black, Asian, Other)
 - Ethnicity (Hispanic/Latino: Yes or No)
 - Baseline Weight (kg)
 - Baseline Height (cm)
 - BMI (kg/m²)
 - Region (Canada, United States, Europe)
- Baseline characteristics:
 - Skin prick test (SPT) for cat (mm)
 - Serum cat dander sIgE and Fel d 1 sIgE at screening and baseline (≥ 0.7 to < 3.5 kUa/L, ≥ 3.5 to < 17.5 kUa/L, ≥ 17.5 kUa/L)
 - Serum house dust mite Df and Dp sIgE at screening and baseline (< 0.7 kUa/L, ≥ 0.7 kUa/L)
 - Baseline sensitization status based on sIgE or SPT (e.g., sensitization to cat allergens only, only sensitized to cat allergens and seasonal allergens, only sensitized to cat allergens and perennial allergens, or sensitized to cat allergens, seasonal and perennial allergens)
 - Baseline sensitization status based on sIgE or SPT (mono-sensitized to cat, poly-sensitized)
 - Baseline allergy symptom status for tree, grass, and weeds (as recorded in eCRF)
 - Baseline TNSS, TOSS, TSS, DMS, CSMS
 - Baseline RQLQ(S)
 - Baseline FEV1(L and percent predicted)
 - History of Asthma (yes/no, as recorded in eCRF)
 - Baseline ANSD, ADSD, ADSS, ACQ-5, asthma rescue medication use, and nighttime awakening for asthma patients

- Baseline PGIS
- Duration of allergic symptoms to cat
- Number of cats in home (1, 2, ≥ 3)

Sensitization status based on sIgE or SPT

An SPT with cat allergen extract, other relevant allergens, a negative control (such as saline/diluent), and a histamine positive control will be performed to assess sensitization status. A positive response for cat is defined by a mean wheal diameter at least 5 mm greater than a negative control, in which SPT mean wheal diameter is defined as $([\text{longest diameter} + \text{longest perpendicular}]/2)$. For other allergens, a positive sensitization by SPT is defined as a mean wheal diameter of at least 3 mm greater than a negative control.

For allergens that are not cat-related, sensitization by sIgE is defined as $\text{sIgE} \geq 0.35$.

SPT and sIgE values will be presented as both summaries of continuous measurements and categorically as specified above. Patients will be considered sensitized to an allergen if they meet the criteria defined above for either SPT or sIgE.

